## SIGNIFICANCE

Overall, we will assess whether immune activation contributes uniquely to CVD risk among HIV-infected women across the reproductive aging spectrum and how statins may reduce CVD risk through effects on this pathway. Answers to these critical questions will influence the development of CVD prediction and prevention strategies tailored to the aging female HIV-infected population worldwide. Maximizing our power to elucidate sex-specific CVD mechanisms in HIV, we will also design, implement, and evaluate the effectiveness of an evidence-based education/awareness recruitment campaign to enhance female enrollment in the REPRIEVE trial. Identification of innovative strategies to recruit women to an interventional clinical trial could have far-reaching practical implications for future trial-based, sex-specific research across disciplines.

## INTEGRATION OF OBJECTIVES INTO A5332

In order to address the objectives above, the REPRIEVE trial protocol has been amended to permit for additional collection of fasting blood stored for assessment of biomarkers at entry, 1 year, and at end of study. The end of study blood draw will facilitate future assessment of whether observed changes in immune markers at 1 year are sustained. Please see A5332 protocol [section 6.1](#), Schedule of Evaluations.

## STATISTICAL CONSIDERATIONS

### Overview Considerations

Overall sample size assumptions: The projected sample size is 5446 persons, or approximately 80% of the total REPRIEVE study sample.

General analysis plans: As comparison groups to address the objectives listed below (eg, groups classified by sex for Objective 1 and by menopause/hormone status for Objective 2) will not have been assigned by randomization, the distributions of baseline characteristics will be compared between groups to help inform the list of characteristics to be included in covariate

.adjusted models specified below. Baseline covariates anticipated to differ by sex (eg, race, hypertension, smoking, substance use, lipids, BMI) [Hattleberg 2014] will be carefully explored and considered, particularly when they are hypothesized to be prognostic for the outcome. Where treatment effect is included in the analysis plan below (eg, statin effect), this variable will use intent-to-treat formulation.

**General monitoring considerations:** Safety of human participants participating in the objectives described will be monitored by the REPRIEVE DSMB as part of the REPRIEVE trial study monitoring plan.

**Outcome Definition, sample size justification, and analysis plans by objective/hypothesis**

**Objective 1:** To assess among HIV-infected individuals ages 40-75 sex-based differences in immune activation and statin-induced immunomodulation in relation to clinical CVD events.

***Hypothesis A)*** *Levels of immune activation markers will be higher in HIV-infected women versus men.* The outcome being tested in this sub-objective is baseline (pre-treatment) immune activation, as measured by the levels of each of select immune activation markers such as sCD14. A non-parametric alternative to t-test (eg, Mann-Whitney test) will compare the pre-treatment distribution of each biomarker between groups assigned by sex. If 22% female enrollment is achieved, then the comparison group sample sizes to address this hypothesis will be 1198 women versus 4248 men (with no adjustments for losses as outcome assessed at baseline). Using these sample sizes and the standard deviations of select biomarkers [Fitch 2013], and adjusting the significance level to 0.0167 by Bonferroni to account for the biomarkers being tested, there will be 90% power to detect sex differences of 214 ng/mL for sCD14. Covariate adjusted models performed as part of the analysis of this hypothesis will use multivariable regression (linear, with log transformation if indicated based on biomarker distribution).

***Hypothesis B)*** *High-level immune activation will relate to CVD events in HIV, and this association will be stronger in women versus men.* The primary outcome being tested in this sub-objective is the composite clinical outcome of MACE occurring at any time during follow-up. The secondary outcome being tested is the time from randomization to first MACE occurring any time during follow-up. High-level immune activation with respect to each tested biomarker will be classified by the observed highest quartile of the pre-treatment distributions. Fisher's exact test will be used for testing the main effect of immune activation. Taking the sample size of 5446 from the overall sample size assumptions above, there is an expectation of 4084 in the low immune activation group and 1362 (highest quartile) in the high immune activation group. Assuming ~6% of the study sample will experience a MACE event (from control arm incidence estimate of 15/1000 person-years and statin effect hazard ratio of 0.70; see REPRIEVE protocol [section 9.0](#) for more details), with sample sizes as above and a Bonferroni-adjusted significance level of 0.0167, there will be 90% statistical power to detect 5% MACE rate in the low immune activation group compared with 7.8% MACE rate in the high immune activation group (ie, absolute difference of 2.8% pts in MACE rate between groups). Assessing whether the association of baseline immune activation and MACE will be higher in women versus men requires testing for an interaction effect between sex and immune activation (high vs. low) for

the outcome of MACE. To assess power for interaction effect, methods described in [VanderWeele 2012] will be used under the following assumptions: 4.9% of men with low immune activation will have a qualifying MACE outcome; the main effect odds ratios (OR) for sex and immune activation are each 2.1 (eg, 4.9% MACE in one group compared with 9.8% in the other); a multiplicative interaction OR of 1.33; association between sex and high/low immune activation of 1.33; and 22% female enrollment. Based on these assumptions and using a significance level adjusted to 0.0167, the statistical power for additive interaction effect (eg, as excess in relative risk attributed to interaction) is estimated as 80%. Testing for interaction effects and covariate adjusted models will use multivariable logistic regression (for the primary outcome) and Cox proportional hazards regression (for the secondary, time- to-event formulation outcome).

*Hypothesis C)* *Statins will decrease levels of immune activation markers to a greater extent in HIV-infected women versus men.* The outcomes being tested in this sub-objective are the changes from pre-treatment to 1 year of follow-up of the immune activation markers tested. For this hypothesis, statistical interactions of sex and treatment effects will be tested using linear (log transformed as indicated) models, which can also incorporate covariate adjustment. With estimates of 5% per year loss to follow-up, the effective sample size for this sub-aim is 5174 persons. For the biomarker sCD14, standard deviation of the outcome measure for this sub-aim is estimated assuming standard deviation of 1-year measurements same as baseline and intra-person correlation of 0.65. Further, assuming under additivity a 125 ng/mL effect of sex on sCD14 differences at 1 year and the same effect of statins on sCD14 differences at 1 year, there will be 80% power to detect an additive interaction effect of 220 ng/mL.

*Hypothesis D)* *CVD risk-reduction will be mediated in part through statin-induced immunomodulation, more so in HIV-infected women versus men.* For this sub-objective, structural equation modeling (SEM) will be employed to investigate the pathways and mechanisms leading to this clinical outcome while incorporating other prognostic factors. Specifically, the SEM model will apply an analysis of covariance structure incorporating multiple biomarker data into a single model for CVD clinical outcome. Furthermore, the model will test the covariates and directionality of effects with CVD outcome, and include temporal ordering. For this sub-objective, some of these pathways include the following: direct effect of sex on CVD, direct effect of sex on immunomodulation, direct effect of immunomodulation on CVD, sex effect on CVD through immunomodulation, direct effect of statin on CVD and on immunomodulation, and sex effect on CVD through statin effect.

*Objective 2:* To characterize among HIV-infected women ages 40-75 how menopause status and ovarian reserve relate to immune activation, statin-induced immunomodulation, and clinical CVD events.

The comparison groups will be formulated by combining hormonal data with data on menstrual history in order to categorize women as pre-menopausal and post-menopausal. Comparison groups will also define the subset of pre-menopausal women with reduced ovarian reserve.

*Hypothesis A)* *Post-menopausal HIV-infected women will have higher levels of immune activation markers versus pre-menopausal HIV-infected women.* As in Objective 1A, the

outcome being tested in this sub-objective is baseline (pre-treatment) immune activation, as measured by levels of certain biomarkers such as sCD14. A non-parametric alternative to t-test (eg, Mann-Whitney test) will compare the pre-treatment distribution of each biomarker within women between groups assigned by menopause status. As per Objective 1A, 22% female enrollment is assumed. Further assuming a 1:1 ratio between female comparison groups, sample sizes for the pre-menopausal and post-menopausal groups will be 599 each. Using these sample sizes, standard deviations for biomarker as in Objective 1A, and Bonferroni-adjusting the significance level to 0.0167, there will be 90% power to detect differences between the pre- and post-menopausal groups of 378 ng/mL for sCD14. Alternatively, if the ratio between female comparison groups is 1:2, sample sizes for the pre-menopausal and post-menopausal group will be 399 and 799, respectively. Under this contingency, the minimal detectable differences between female comparison groups for 90% power are only slightly higher at 401 ng/mL.

*Hypothesis B)* *Among both pre- and post-menopausal HIV-infected women, reduced ovarian reserve (undetectable AMH) will relate to risk of first CVD event.* As in Objective 1B: The primary outcome being tested in this sub-objective is the same composite clinical outcome of MACE occurring any time during follow-up. The secondary outcome being tested is the time from randomization to first MACE. Assuming 22% female enrollment in REPRIEVE and that a negligible proportion of the pre-menopausal women have reduced ovarian reserve such that the ratio of women with adequate versus reduced ovarian reserve is 1:1, then sample sizes for each group will be 599. As per Objective 1B, it is assumed that the overall rate of MACE among women will be 7%. Applying this event rate with the sample sizes above and using Fisher's exact test for analysis, there will be 90% power (at 5% significance) to show a difference of 5% points between groups (namely, 4.5% MACE in one group and 9.4% MACE in the other.) Alternatively, if a significant proportion of the pre-menopausal women have reduced ovarian reserve such that the ratio of women with adequate versus reduced ovarian reserve is 1:4, then sample sizes will be 299 for the adequate ovarian reserve group and 898 for the reduced ovarian reserve group. In this scenario, there will be 90% power to show a difference of 5.7% between groups. Covariate adjusted models for this hypothesis will use multivariable logistic regression for the primary outcome formulation, and Cox proportional hazards modeling for the time-to-initial event formulation.

*Hypothesis C)* *Statins will decrease levels of immune activation markers to a greater extent in post-menopausal HIV-infected women versus pre-menopausal HIV-infected women.* The outcomes being tested in this sub-objective are the changes from pre-treatment to 1 year of follow-up of each of the immune activation markers tested parallel to Objective 1C. Interactions by menopause status and treatment will be tested using linear (log transformed as indicated) models, which can also incorporate covariate adjustment. Assuming a 22% female enrollment and a 5% per year loss to follow up, the effective sample size for this analysis is 1138. Assuming a 1:1 ratio of female comparison groups, the sample sizes will be 569 for the pre- and post-menopausal groups. Using analysis assumptions from Objective 1C, and under additivity assuming a 375 ng/mL effect of menopause on sCD14 differences at 1 year as well as a similar effect of statins on sCD14 differences at 1 year, there will be 80% power to detect an additive interaction of menopause and statin of 390 ng/mL.

Hypothesis D) CVD risk-reduction will be mediated in part through statin-induced immunomodulation, more so in post-menopausal (vs. pre-menopausal) HIV-infected women. Parallel to Objective 1D, the SEM model will be used to incorporate all biomarker data into a single model for CVD clinical outcome, and then to test the covariate pathways, including directionality and temporal ordering. For this sub-objective, some of these pathways to be tested include the following: direct effect of menopause status on CVD, direct effect of menopause status on immunomodulation, direct effect of immunomodulation on CVD, menopause effect on CVD through immunomodulation, direct effect of statin on CVD and on immunomodulation, and menopause effect on CVD through statin effect.

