## 9.6 Analyses

### 9.6.1 General Analysis Considerations

The following sections provide a brief overview of the analysis considerations for REPRIEVE (A5332). Prior to the start of enrollment, a detailed Statistical Analysis Plan fully delineates all planned statistical analyses. **In the event of a DSMB recommendation to stop the trial for efficacy at interim review, full analysis and publication of the primary trial results will be prepared based on the frozen data for the DSMB meeting. Subsequent analyses (including a database prepared for future data-sharing requests) will be performed based on the final trial database including all final study termination visits. In the event of a DSMB recommendation to stop for futility, full analysis and publication of the primary trial results will be performed based on the final trial database including all final study termination visits.**

All major treatment comparisons between the randomized groups will be performed according to the principle of "intention-to-treat;" that is, participants will be analyzed (and endpoints attributed) according to the randomized treatment assigned regardless of subsequent changes to that treatment; as-treated analyses will also be performed. Descriptive summaries of the distribution of continuous baseline variables will be presented in terms of percentiles (eg, median, 25th and 75th percentiles), while discrete variables will be summarized in terms of frequencies and percentages. Statistical comparisons will be performed using two-sided significance tests with a 5% Type I error.

Unless otherwise noted, comparison of time to event outcomes will use methods for competing risks, notably Cox proportional hazards models for estimation of cause-specific hazard ratios and Gray's test for comparison of cumulative incidence curves.

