### OBJECTIVES

#### OBJECTIVE 1: To assess among HIV-infected individuals ages 40-75 sex-based differences in immune activation and statin-induced immunomodulation in relation to clinical CVD events.

In order to achieve this objective, we will add to the REPRIEVE trial blood sample collection on female and male participants and sample processing for immune activation markers relevant to atherogenesis in HIV (beginning with monocyte activation markers including sCD14, and then exploring other immune activation markers). HYPOTHESES: Baseline relationships: A) Levels of immune activation markers will be higher in HIV-infected women versus men. B) High-level immune activation will relate to CVD events in HIV, and this association will be stronger in women versus men. Statin effects: C) Statins will decrease levels of immune activation markers to a greater extent in HIV-infected women versus men. D) CVD risk-reduction will be mediated in part through statin-induced immunomodulation, more so in HIV-infected women versus men.

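### Optional efficiency gain: in Appendix IV, Holm's step-down procedure could replace single-step Bonferroni at 0.0167, with the same 5% family-wise error and never fewer rejections

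*Protocol*

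**What the plan says.** Protocol Appendix IV (sex-specific mechanisms), Statistical Considerations, sets the level for the marker comparisons inside its power statements.

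- **Objective 1, Hypothesis A** (women versus men at baseline) compares each marker by a Mann-Whitney type test, "adjusting the significance level to 0.0167 by Bonferroni to account for the biomarkers being tested". On that basis "there will be 90% power to detect sex differences of 214 ng/mL for sCD14".
- **Objective 1, Hypothesis B** (high versus low marker level and MACE) uses "a Bonferroni-adjusted significance level of 0.0167" for the main effect, with 90% power. The sex-by-marker interaction uses the same level, with 80% power.
- **Objective 2, Hypothesis A** (pre- versus post-menopausal women) again gives its 90% power after "Bonferroni-adjusting the significance level to 0.0167".

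The number of markers is not given. Hypothesis 1A describes its outcome "as measured by the levels of each of select immune activation markers such as sCD14", and the statement of Objective 1 describes the work as "beginning with monocyte activation markers including sCD14, and then exploring other immune activation markers". Appendix IV mentions no step-down or other sequential rule. Section 9.6.1 of the main protocol states the general standard: "Statistical comparisons will be performed using two-sided significance tests with a 5% Type I error".

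**The concern.** Read as a decision rule, a single-step level holds every marker to 0.0167 whatever the other markers show. Once one marker has been rejected at 0.0167, at most two true null hypotheses can remain among three. The next marker could then be tested at 0.025 and the last at 0.05 without raising the family-wise error above 5%. Holm's procedure does exactly this. It rejects everything Bonferroni rejects and sometimes more.

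At stake is the power to declare the second and third markers. That has some relevance because Hypotheses 1A and 2A are worded in the plural, about markers rather than about sCD14 alone. These are ancillary objectives, and neither the MACE result nor the Mechanistic Substudy result depends on them.

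**Working it through.** **Inputs.** Level 0.0167; power 90% for sCD14 at 214 ng/mL; "the comparison group sample sizes to address this hypothesis will be 1198 women versus 4248 men" (all Hypothesis 1A). Two-sided 5% comes from section 9.6.1. Four things are assumed because the documents do not give them: three markers, 90% power at 0.0167 for each marker with a real effect, z-type test statistics, and the correlation between those statistics (shown over a range).

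**1. The plan's own figures.**
- 0.05/3 = 0.0167.
- z for two-sided 0.05/3 is 2.394 and z for 90% power is 1.282. Their sum, 3.676, is the mean of the test statistic.
- The SD of sCD14 is not stated. Solving difference = 3.676 × SD × √(1/n₁ + 1/n₂) gives an SD of about 1780 ng/mL from 214 (1198 vs 4248), from 378 (599 vs 599) and from 401 (399 vs 799). With that SD, 1A has 90.0% power at 214 ng/mL.
- The 1B main effect (5% vs 7.8%, 4084 vs 1362, level 0.0167) gives 90.7% by the normal approximation, against 90% stated.

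The stated powers are consistent with each other.

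**2. Marginal power at the three Holm levels.** Φ(3.676 − z) is 90.0% at 0.0167, 92.4% at 0.025 and 95.7% at 0.05. So one marker's p-value falls at or below 0.0167 with probability q₁ = 0.900, between 0.0167 and 0.025 with q₂ = 0.0242, and between 0.025 and 0.05 with q₃ = 0.0326.

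**3. All three effects real, independent statistics.**
- Bonferroni: 0.90³ = 72.9%.
- Holm needs the smallest p ≤ 0.0167, the second ≤ 0.025 and the largest ≤ 0.05: q₁³ + 3q₁²q₂ + 3q₁²q₃ + 3q₁q₂² + 6q₁q₂q₃ = 0.7290 + 0.0589 + 0.0793 + 0.0016 + 0.0043 = 87.3%.
- Average power per marker rises from 90.0% to 95.2%.

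**4. All three effects real, correlated statistics (simulation).**

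| Common correlation | Bonferroni, all three | Holm, all three |
|---|---|---|
| 0 | 73% | 87% |
| 0.5 | 78% | 89% |
| 0.9 | 85% | 92% |
| 1.0 | 90% | 90% |

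**5. Fewer real effects (independent).**
- Two real: declaring both goes from 0.90² = 81% to 86% (85.5%), and average power from 90.0% to 92.3%.
- One real: its power goes from 90.0% to 90.1%.
- At least one declared: identical under both rules, because both begin by testing the smallest p-value at 0.0167. With three real effects it is 1 − 0.1³ = 99.9%.

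**6. Lower per-marker power.** At 80%, the figure stated for the 1B interaction, declaring all three goes from 0.80³ = 51% to 72% with three real independent effects.

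**7. Error control.** With all three nulls true and independent, both rules give 1 − (1 − 0.05/3)³ = 4.9%. Simulated Holm family-wise error was 5.0% or less, within simulation error, in every mixture of true and false nulls tried.

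**The case against.** **Nothing is wrong with the plan as it stands.** Bonferroni controls the error rate and the quoted powers are right for it. This stands, and it is why the point is optional.

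**The 0.0167 appears only in power statements.** The sentences that name the tests give no multiplicity rule, so powering at 0.0167 and later analysing with Holm would not contradict the text. That is fair. It remains true that the appendix offers no other rule, so a reader would take 0.0167 as the working one.

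**The largest gain is the favourable case.** It needs three markers, all effects real at the design size, and independence. Independence is doubtful when the first markers come from one pathway, monocyte activation. No passage requires all three markers to be declared. This stands, and the gain has to be quoted with those conditions.

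**Bonferroni has a practical merit.** Its tests and confidence intervals agree, and section 9.6.1 promises extensive use of intervals. Under Holm, a last-ranked marker with p = 0.03 could be rejected while its Bonferroni-level interval includes no difference. This is a real but small cost.

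**Stronger readings that a reader might infer, and that the documents do not support.**
- *Power is lost on every marker.* It is not: Holm also tests the smallest p-value at 0.0167.
- *The 5% control fails because the marker list is open.* Holding 0.0167 fixed would give 1 − (1 − 0.0167)⁶ = 9.6% for six independent markers and 15.5% for ten, but no passage says that 0.0167 would be kept for a longer list. The text ties the adjustment to the markers tested and describes the later ones as being explored.

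**Conclusion.** The point holds as an optional efficiency improvement. Holm keeps the same 5% family-wise error under any dependence and never rejects less. Its benefit falls on the second and third markers, and its size depends on the truth: about 14 percentage points on declaring all three if three effects are real and independent, about 11 at correlation 0.5, about 7 at 0.9, about 5 on declaring both if only two are real, and essentially none if one is real or the markers are perfectly correlated.

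These figures rest on two things the appendix does not state: that there are three markers (inferred from 0.05/3) and that each real effect has 90% power at 0.0167 (stated only for sCD14). The result is no evidence of an invalid test, an inflated error rate or a wrong sample size.

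**What to change.** In Appendix IV, Hypotheses 1A, 1B (main effect and interaction) and 2A:

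- Name the confirmatory markers.
- Within each hypothesis, test them by Holm's step-down procedure at family-wise 5%. With three markers: smallest p at 0.0167, next at 0.025, last at 0.05, stopping at the first failure.
- State that markers added later are exploratory.
- Keep the stated powers as lower bounds: 90% for 1A, the 1B main effect and 2A, and 80% for the 1B interaction.
- Report intervals at the Bonferroni level, noting that one may occasionally include no difference for a marker that Holm rejects.

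The cost is a few sentences, with no new data and no change in sample size. The change should be made before the marker comparisons are run.

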9.2.3.2 Time to heart failure

9.3 Randomization and Stratification

At study entry, participants will be assigned with equal probability to one of the two treatment arms. Randomization will use permuted blocks with stratification by sex (male/female) and screening CD4+ T-cell counts ( $\leq 500$  vs.  $> 500$  cells/mm $^3$ ). Additionally, to ensure balanced treatment allocation for the Mechanistic Substudy of REPRIEVE (A5333s), randomization will also be stratified by whether or not a participant has elected to participate in the mechanistic substudy (yes/no). Total enrollment of individuals with low cardiovascular risk (10-year ASCVD risk score  $< 5.0\%$ ) was capped at approximately 4200 participants, to ensure that the final study population reflects the targeted low-to-moderate risk population. It is anticipated that the study will take 48 months to fully enroll.

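### Appendix IV, Objectives 1B and 2B: the primary analyses of MACE ignore observation time, so any follow-up difference between the non-randomised groups would be read as a difference in risk; the planned Cox analysis should be primary

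*Protocol*

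**What the plan says.** Appendix IV, Objective 1, Hypothesis B relates high baseline immune activation (top quartile of each biomarker) to MACE, and asks whether the association is stronger in women. On the outcome it states: "The primary outcome being tested in this sub-objective is the composite clinical outcome of MACE occurring at any time during follow-up". The time-to-event version is ranked second: "The secondary outcome being tested is the time from randomization to first MACE occurring any time during follow-up". For the main effect, "Fisher's exact test will be used for testing the main effect of immune activation". The sex-by-activation interaction and the adjusted models use logistic regression for the primary outcome and Cox regression for the secondary one.

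Objective 2, Hypothesis B (adequate versus reduced ovarian reserve, women only) uses the same outcomes and methods in the same order. Neither objective gives the binary analysis a fixed horizon, an offset or a person-time term.

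Four other parts of the protocol bear on this:
- **Follow-up.** Section 9.4.1 gave individual follow-up of 3.5 to 6 years and assumed 5% loss per year. Section 9.3 now says "It is anticipated that the study will take 48 months to fully enroll", and section 9.1 closes the study when 288 primary events are reached.
- **Grouping.** The general analysis plan in Appendix IV acknowledges that the comparison groups are not formed by randomisation.
- **Accrual.** Sections 2.1.5 to 2.1.7 and 3.0 describe raised risk-score ceilings and later caps on low-risk enrolment.
- **Main-protocol analysis.** Section 9.6.3 uses Cox models of the cause-specific hazard for risk factors and selected biomarkers. Logistic regression appears there only as an alternative under case-control sampling.

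The SAP supplied covers the mechanistic substudy and does not address these analyses.

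**The concern.** A yes/no outcome counted over whatever follow-up each person happens to have mixes the event rate with the time observed. With 48 months of accrual and a common close, the earliest and latest entrants differ by about 4 years of potential follow-up. If high-activation or low-reserve participants tended to enter earlier or later, or left observation at a different rate, Fisher's test and logistic regression would attribute the resulting difference in event counts to the biomarker.

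Randomisation does not protect these comparisons. The changes in ceilings and caps mean that the type of participant enrolled changed over calendar time. Adjustment is described for baseline characteristics only, which does not cover time observed. Non-CVD deaths, which section 9.2.1 treats as competing events, simply count as no MACE in the binary analysis.

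At stake are the primary tests of two ancillary hypotheses. The randomised comparison of pitavastatin with placebo is unaffected: section 9.6.2 already analyses it by cause-specific Cox regression.

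**Working it through.** **Inputs (1B).** Low activation n = 4084, high n = 1362, total 5446; alpha 0.0167; MACE 5% versus 7.8%; stated power 90%. Two-sided testing is taken from section 9.6.1. The event-rate basis is 15/1000 PY in controls with HR 0.70, so the pooled rate with equal arms is (15 + 0.70 × 15)/2 = 12.75/1000 PY.

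**Reproducing the stated power.** Two-proportion normal approximation:
- Pooled risk: (4084 × 0.05 + 1362 × 0.078)/5446 = 310.4/5446 = 0.057.
- Null SE: √[0.057 × 0.943 × (1/4084 + 1/1362)] = 0.00725. Alternative SE: √[0.05 × 0.95/4084 + 0.078 × 0.922/1362] = 0.00803.
- z = (0.028 − 2.393 × 0.00725)/0.00803 = 1.33, so power is 90.7%. Simulated Fisher power is 90.4–90.9%. The stated 90% is reproduced.

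**What follow-up alone can do.** Cumulative risk is 1 − exp(−0.01275 t): 4.4% at 3.5 years and 7.4% at 6 years. That 3.0-point spread is slightly more than the 2.8 points the test is powered to detect. It compares the two ends of the follow-up range and is not a plausible gap between group means. For a 1-year gap in means (4.5 versus 5.5 years), risks are 5.58% and 6.77%, odds ratio 1.23. For 0.5 year they are 5.73% and 6.33%, odds ratio 1.11.

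**False-positive rate with identical hazards** (12.75/1000 PY in both groups, nominal 1.67%, 4000 simulated trials per row, simulation SE about 0.2 points at the nominal level). In the rows with a gap, the high-activation group is followed longer.

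| Follow-up in years, low / high group | Fisher | Test using time |
|---|---|---|
| 3.5–6 / 3.5–6 | 1.9% | 2.0% (log-rank) |
| 4–8 / 4–8 | 1.4% | 1.6% (log-rank) |
| 3.375–5.875 / 3.875–6.375 (gap 0.5) | 5.5% | 1.6% (log-rank) |
| 3.25–5.75 / 4.25–6.75 (gap 1) | 20.7% | 1.5% (log-rank) |
| 3.75–7.75 / 4.75–8.75 (gap 1) | 17.1% | 1.7% (log-rank) |
| 3.5–6 / 4–6.5, with 5% annual loss (gap 0.5) | 3.7% | 1.6% (rate ratio) |
| 3.5–7.5 / 4.5–8.5, with 5% annual loss (gap 1) | 10.6% | 1.8% (rate ratio) |

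Treating every participant as followed for the group mean, without loss, gives 4.6–5.8% for 0.5 year and 16.5–21.4% for 1 year. Overall the ranges are about 4–6% and 11–21%.

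**Power if time to event is primary.** The implied HR is ln(1 − 0.078)/ln(1 − 0.05) = 1.58, with about 310 events. Schoenfeld: √(310.4 × 0.2501 × 0.7499) × ln 1.58 − 2.393 = 3.51 − 2.39 = 1.11, so 86.7%. Simulated log-rank power with follow-up uniform on 3.5–6 years is 91.4%, against 90.4% for Fisher.

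Objective 2B (599 versus 599, alpha 5%) was not simulated. The mechanism is the same but the percentages above do not carry over.

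**The case against.** The strongest objection is that staggered entry does no harm by itself. This stands: with the same follow-up distribution in both groups, Fisher's error was 1.4–1.9% against 1.67%, and power was within about a point of log-rank. A reader might infer from the multi-year spread that the primary test is biased. The documents do not support that, because no section reports a follow-up difference between the compared groups. The 0.5 and 1 year gaps are assumptions, and the direction of any gap is unknown.

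A reader might also infer that women enrolled later, given the planned "recruitment campaign to enhance female enrollment in the REPRIEVE trial", and that this distorts the sex interaction. The protocol gives no dates or results for the campaign, and the effect on the logistic interaction would be negligible. Assume a low-group hazard of 10/1000 PY, HR 1.6 in both sexes, men followed 6 years and women 5. The odds ratios are (e^0.096 − 1)/(e^0.06 − 1) = 1.629 and (e^0.08 − 1)/(e^0.05 − 1) = 1.624, a ratio of 0.997. An additive measure would shift more; that was not computed. Objective 2B compares women with women, so the campaign does not bear on it directly.

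Differential loss is a weaker argument than differential entry. The protocol gives one overall rate of 5% per year. Assuming 7% in the high-activation group and 4% in the low group over 6 years, a true HR of 1.6 becomes a risk ratio of 1.44, an attenuation rather than a false confirmation. Endpoint information is also sought after discontinuation unless consent is withdrawn (sections 6.3.10 and 8.2).

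Finally, the Cox analysis is already prespecified, so a discrepancy would be visible, and these are ancillary objectives. Both points are true and limit the severity. They do not explain why the analysis that ignores time is the primary one.

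**Conclusion.** The concern holds conditionally. Objectives 1B and 2B rank an analysis that takes no account of observation time above one that does, although the groups are observational and follow-up varies by years. Any difference in follow-up between groups would be read as a difference in risk. In 1B, if hazards are equal at 12.75/1000 PY, a 0.5-year gap in mean follow-up would put Fisher's false-positive rate at about 4–6%, and a 1-year gap at about 11–21%, against a nominal 1.67%. With no gap there is no inflation.

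A gap is plausible because ceilings and caps changed who was enrolled over time, but it is not documented. Nor should Cox regression be taken as an unbiased alternative: it corrects for differing observation time, while confounding between non-randomised groups and loss related to risk would remain. The change is worth making because it is cheap and matches section 9.6.3, not because bias has been shown.

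**What to change.** In Appendix IV, Objectives 1B and 2B, make time to first MACE by cause-specific Cox regression the primary analysis, with the sex-by-activation interaction term in 1B. Keep any MACE during follow-up, by Fisher's exact test and logistic regression, as secondary. No new data or methods are needed.

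The cost is in the power statements:
- The 90% main-effect power in 1B becomes about 87% (Schoenfeld) to 91% (simulation) under the appendix's own event assumptions.
- The 80% additive-interaction power in 1B rests on binary risks and odds ratios and must be recalculated for the Cox analysis, not merely annotated.
- The 90% power in 2B should be restated on the same basis.

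The restatement should also use the current event target, whichever analysis is primary. The roughly 310 events implied for 5446 people exceed the 288 planned for the whole trial. A proportional share is 288 × 5446/7500 = 209 events, for which Schoenfeld power at HR 1.58 is about 69%.
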